- Within-host variation in influenza strains between the first and the third viral swab
- Cost effectiveness, assessed using health resource utilization (visit to clinic, hospital, pharmacy, emergency department) and school and work absenteeism
- Proportion with antiviral resistance, assessed by genetic sequencing of influenza strains from the drug eligible and drug ineligible study participants

Hypothesis

Primary hypothesis:

- A home-based approach to influenza infection control will result in a large percentage of drug eligible individuals diagnosed with influenza initiating antiviral therapy within 48 hours of symptom onset.

Secondary hypotheses:

- Home-based approach to influenza infection control and rapid delivery of antiviral therapy will decrease symptom severity in the drug eligible individuals diagnosed with influenza that administer antiviral therapy within 48 hours of symptom onset compared to drug eligible, influenza-infected individuals that administer antiviral therapy greater than 48 hours after symptom onset.
- Home-based approach to influenza infection control and rapid delivery of antiviral therapy will decrease the duration of viral RNA detection in the drug eligible, influenza-infected individuals that administer antiviral therapy within 48 hours of symptom onset compared to drug eligible, influenza-infected individuals that administer antiviral therapy greater than 48 hours after symptom onset.

IV. Study Population

The study will be conducted in households with at least 3 members, where at least 2 of these members must be eligible to receive BXM, in the Seattle area. Participants aged 12 years or older, weighing at least 40 kg, will be drug eligible. Participants of any age that reside in the same household as the case at least 4 days per calendar week will be drug ineligible study participants. Drug eligible study participants will receive baloxavir intervention when appropriate,

and all drug eligible and drug ineligible participants will receive a 7-day follow-up from the study team per illness episode.

Study size

The study is being conducted in the Seattle, WA area over one influenza season. The goal is to enroll 250 households, with enrollment occurring prior to and during the annual influenza season.

Household enrollment criteria

The household must meet all the following enrollment criteria:

Household inclusion criteria

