All sick individuals, meaning those drug eligible and those drug ineligible, will complete an illness questionnaire in REDCap 7 days after they report the illness. This questionnaire will collect information on the presence or absence of respiratory and systemic symptoms during the 7 days after reporting the illness. Data will also be collected on childcare, school, and work absenteeism, and subsequent visits to health care providers. Additionally, the influenza-diagnosed individual will provide nasal swab specimens collected via self-swab or parent/legal guardian-swab at Study day 2-3 and Study day 5-7. These swabs will be returned to the laboratory via a delivery services the day of or the day after collection (See VI. Laboratory Procedures section). In addition to the illness questionnaire, the drug eligible, influenza infected participant will complete a standard questionnaire at 7 and 14 days following study drug receipt to monitor for the occurrence of adverse events (AEs) or serious adverse events (SAEs). These questionnaires will be monitored by a member of the study team. Additionally, any provider consultations with tele-health following drug administration will be reported to the study team to monitor for the occurrence of adverse events (AEs) or (SAEs). Any reported adverse events will be assessed to determine if related to drug treatment and whether unexpected or not and subsequently reported to the IRB using a standardized AE and SAE form. After the self-collected nasal swabs have been tested in the laboratory, the case will have to ability to view the results of their swab on the Seattle Flu Study website.

For all individuals that provide nasal swab specimens for testing and further characterization, they will have the ability to view whether influenza or respiratory syncytial virus (RSV) was detected from their swab(s) on the Seattle Flu Study website (See VI. Laboratory Procedures).

Data collection

Data will be collected electronically in REDCap online via a computer or mobile device or through a text-message accessible app. The major data collection activities will occur at the following times (See Table 1).

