 - **If influenza is not diagnosed**, the sick participant will provide one nasal swab collected via self-swab or parent/permanent legal guardian-swab, which will be mailed back to the laboratory. Additionally, the ill participant will complete an illness questionnaire at Study day 0, then again at Study day 7. The household will remain enrolled and continue to monitor for the development of a cough or 2 or more respiratory symptoms via the weekly symptom monitoring log.
 - **If influenza is diagnosed**, ill participant will provide a nasal swab sample collected via self-swab or parent/legal guardian-swab. Also, following a positive test result, the ill participant will complete Study day 0 of the illness questionnaire. This questionnaire will collect information regarding the presence, duration, and severity of respiratory and systemic symptoms in the ill participant. Additional information such as recent travel history, childcare, school, or work absenteeism as well as data on subsequent medical care will be collected on the questionnaire. Additionally, the 98point6 provider will confirm antiviral treatment is appropriate, and write a BXM prescription. Next, BXM will be delivered home of the case within 6 hours via a rapid delivery service.
- **Following delivery and therapy initiation**, the case will document the time of consumption.
- **At Study day 2-3 and Study day 5-7 after a positive test result**, the drug eligible, influenza-infected participant will provide nasal swab samples collected via self-swab or parent/legal guardian-swab. All nasal swabs will be mailed back to the laboratory for further testing the same day or the day following collection (see VI. Laboratory Procedures section). Also, the ill participant will complete an illness questionnaire 7 days after antiviral treatment. This questionnaire will collect information regarding the presence, duration, and severity of respiratory and systemic symptoms. Additional information such as recent travel history, childcare, school, or work absenteeism as well as data on subsequent medical care will be collected through the questionnaire.
- **Within 48 hours after drug receipt**, individuals will be screened for evidence of reaction to the drug using a standardized questionnaire in REDCap.

- **7 days and 14 days after drug receipt**, individuals will be screened for evidence of reaction to the drug using a standardized questionnaire.

Table 1. Timing of Data Collection

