Protection against risks

All identifying data will be stored at the University of Washington using standard security techniques. Hard copies of data collection materials that have identifiers will be locked in the office of the study PI or a room with limited access by specific individuals. When possible, redacted (de-identified) versions of the data will be used for coding and data analysis. Personal identifiers will be stored in the database on a password protected network that is HIPAA-compliant, and only accessible to specific individuals. Transfer or storage on portable devices

(e.g., laptops, flashdrives) will be encrypted. The devices on which this information is stored will be accessible only to individuals who need access to the data.

The project will be approved by the Institutional Review Board (IRB) at the University of Washington. This study will be conducted according to Good Clinical Practice (GCP) guidelines at that are appropriate for use of already approved drugs. We will appoint an independent Safety Officer who is not involved in this study.

To reduce distress, study participants will be given the opportunity to skip any questions that they are not comfortable answering. Additionally, all participants will be reminded that participating in research is always optional, and they may terminate their participation at any time without consequences. All members of the research team will be required to complete the Good Clinical Practice (GCP) and the Protecting Human Research Participants training offered before enrollment of participants begins. Only those research team members with login credentials and passwords will be granted access to the centralized data capture system, where data are stored and audited. As previously stated, to mask participant identity, participants will be assigned unique study identifiers (participant ID numbers) at the time of enrollment. Only specific members of the study team and the study pharmacist (for cases) will be able to link to the participant ID to the participant's name.

Future Use

As the genome of influenza viruses (and other respiratory viruses) can change even within a season, it is critical that backup samples be kept that can be used with the latest primers to account for this drift. The samples will be held in a freezer at the University of Washington to serve as this backup.

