For the secondary endpoints of symptom duration and severity, drug eligible and drug ineligible participants will be analyzed separately. Symptom severity will be measured on a 4-point scale (0 = no symptoms, 1 = mild, 2 = moderate, 3 = severe) for each influenza-associated symptom the participant reports experiencing. Influenza-associated symptoms the participant does not report as experiencing will be coded as 0. An additional analysis will be conducted comparing secondary endpoints for drug eligible, influenza-infected study participants that received and initiated treatment within 48 hours of symptom onset and those that initiated treatment later than 48 hours. Kaplan-Meier curves will be used to present and analyze time to resolution of symptoms, defined as the time when the influenza-positive participant reports experiencing no respiratory or systemic symptoms. For study participants who received BXM, a Cox proportional hazards model will be used to calculate the hazard ratio, 95% confidence interval, and p-value for symptom duration by group (therapy within 48 hours of symptom onset, and therapy after 48 hours of symptom onset). The analysis of drug ineligible study participants will use a similar approach but will cluster by household and use a robust variance for computing confidence intervals and p-values. For BXM recipients, symptom severity will be compared between groups (therapy within 48 hours of symptom onset, and therapy after 48 hours of symptom onset) using proportions for categorical measures of severity and Pearson's chi-square test, as well as using ordinal regression. As above, the analysis using ordinal regression of drug ineligible study participants will cluster by household and use a robust variance for computing confidence intervals and p-values.

For the secondary endpoints of maximum viral titer and duration of viral RNA detection, we will use t-tests or nonparametric alternatives and linear regression to assess maximum viral titer and Kaplan-Meier curves and Cox proportional hazards models to assess duration of viral RNA detection.

Interim Analysis

This study is being conducted over the course of one influenza season. Therefore, an interim analysis will not be performed.

Antiviral resistance analysis

The secondary outcome data regarding emergence of BXM resistance will be reviewed at the end of the influenza season via genome sequencing of the viral RNA.

Health economic analysis

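### The severity comparison of early v later baloxavir omits the Day 0 severity that the study already collects, so it is open to confounding by initial severity

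*Protocol*

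**What the plan says.** Protocol III (Hypothesis) states that home-based care with rapid delivery "will decrease symptom severity in the drug eligible individuals diagnosed with influenza that administer antiviral therapy within 48 hours of symptom onset", relative to infected drug-eligible participants treated later.

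Protocol XI defines the outcome: "Symptom severity will be measured on a 4-point scale (0 = no symptoms, 1 = mild, 2 = moderate, 3 = severe", rated for each influenza-associated symptom the participant reports, and then "Influenza-associated symptoms the participant does not report as experiencing will be coded as 0". For baloxavir recipients, "symptom severity will be compared between groups (therapy within 48 hours of symptom onset, and therapy after 48 hours of symptom onset", by proportions with Pearson's chi-square and by ordinal regression. It names no covariate, assessment day, post-dose window or per-person summary. Earlier in the same section, symptom severity is one of the factors in the log-binomial model for starting treatment within 48 hours.

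Protocol V (Data collection) says of drug-eligible participants diagnosed with influenza that "following a positive test result, the ill participant will complete Study day 0 of the illness questionnaire", and "This questionnaire will collect information regarding the presence, duration, and severity of respiratory and systemic symptoms in the ill participant". Prescription and delivery come later in that list.

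The follow-up form is anchored in two ways. Protocol V (Follow-up) has it cover "presence or absence of respiratory and systemic symptoms during the 7 days after reporting the illness". Protocol V (Data collection) places a form that includes severity 7 days after antiviral treatment.

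On missing answers, Protocol VIII says that "study participants will be given the opportunity to skip any questions that they are not comfortable answering", and also provides weekly checks and queries for missing values. SAP B1 excludes anyone with no symptom questionnaire. SAP B3 lists severity for each symptomatic day, for descriptive Table 1b only. The SAP contains no severity model.

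**The concern.** The two groups are not randomised. People fall into them according to how soon they noticed symptoms, tested, consulted and took the drug, and how ill they felt may influence each of these steps. The protocol allows for this when it models timely treatment on severity, but it makes no such allowance when severity becomes the outcome.

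If the early group starts sicker, an unadjusted comparison can hide a benefit. If the late group starts sicker, it can create one. The documents do not say which is more likely. A rating that would reduce the problem is already collected.

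**Working it through.** **Plan's own figures.** The documents give no sample size, effect size or power for severity. The only related figure is the expected number of cases: 250 x 0.25 = 62.5, stated as 63. Only one person per household can receive baloxavir, so about 63 is a ceiling for treated confirmed cases. It is lower if some first cases are drug-ineligible.

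**Is Day 0 severity pre-dose?** Protocol V (Onset of Symptoms, drug-eligible list) puts the Day 0 form at step 2, the telehealth contact at step 3 (concurrent), dispensing and delivery at steps 5-7, and ingestion at step 8. The listed order is pre-dose. Ingestion time is recorded, so this can be checked for each participant.

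**Effect of leaving it out (illustration).** Assumptions, none from the documents: no drug effect; n = 63 split 47 early and 16 late; Day 0 severity higher in the early group by d SD; Day 0-outcome correlation r; normal outcomes and linear models standing in for the ordinal model; 2,000 runs. The expected false difference without adjustment is r x d.

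| r | d | r x d (SD) | Unadjusted rejection | Adjusted rejection |
|---|---|---|---|---|
| 0.3 | 0.3 | 0.09 | 5.5% | 4.3% |
| 0.3 | 0.5 | 0.15 | 8.7% | 5.7% |
| 0.5 | 0.3 | 0.15 | 8.2% | 4.4% |
| 0.5 | 0.5 | 0.25 | 13.4% | 5.0% |
| 0.7 | 0.3 | 0.21 | 10.4% | 4.4% |
| 0.7 | 0.5 | 0.35 | 23.7% | 4.6% |

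The simulated false differences were 0.08-0.35 SD without adjustment and about 0 with it. With d = 0, both analyses reject about 4%-5.5% of the time. In the linear model, adjustment leaves 1 - r^2 of the residual variance: 0.91, 0.75 or 0.51 at r = 0.3, 0.5 or 0.7.

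**Window.** The share of a 7-day (168-hour) recall period that falls before the dose, if the period starts at the illness report:
- With the 2-6 hour delivery lag in Protocol V and diagnosis at the time of report: 2/168 = 1.2% to 6/168 = 3.6%.
- With assumed delays of 24 and 48 hours: 24/168 = 14% and 48/168 = 29%.

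**Skipped items coded 0 (illustration).** Assume that 60% of participants are truly moderate or worse in both groups:
- Skip rates of 5% early and 20% late: 0.60 x 0.95 = 57% v 0.60 x 0.80 = 48%, a false gap of 9 points.
- Skip rates of 10% and 30%: 54% v 42%, a gap of 12 points.
- Equal 10% rates: 54% v 54%, no gap.

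**Size of the late group.** Drug qualification requires symptoms for less than 48 hours. If delivery takes 6 hours and the drug is taken on receipt, only people diagnosed later than 48 - 6 = 42 hours after onset are treated late. With 2 hours, the figure is 46.

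**The case against.** Three stronger readings are tempting, and the documents do not support them.

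- **The score mixes pre-dose with post-dose severity.** A reader might infer this from the recall period in Protocol V (Follow-up). That sentence concerns presence or absence of symptoms. The Data collection text that mentions severity sets the form 7 days after treatment and gives no recall period. Section XI names neither a window nor a worst-score summary. If the delivery lag is the only pre-dose time, it is 1%-4% of the week. What stands is that no post-dose window is defined and the two anchors conflict.
- **Non-response is scored as the best outcome.** Coding an unendorsed symptom as 0 is an ordinary checklist rule. Wholly missing questionnaires lead to exclusion, and missing values are queried. The statement about skipping is general and gives no evidence that symptom items go unanswered. What stands is that the rule does not separate skipped from absent symptoms, and that someone with a Day 0 form but no Day 7 form is not covered.
- **The plan ignores initial severity altogether.** It does not: severity, with the day unstated, is a factor in the model for timely treatment. The omission is confined to the comparison with severity as outcome.

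It is also fair to say that this is an additional analysis in a feasibility pilot, and that no covariate can rescue a contrast with very few late-treated people. That limits what the result can show. It is not a reason to leave out a baseline value already in hand.

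**Conclusion.** The point holds in this form: a stated hypothesis is tested by an unadjusted comparison of self-selected groups, although a pre-dose measure of the same outcome is collected and the protocol itself regards severity as a possible predictor of group membership. The window and the coding of skipped items are secondary gaps in specification.

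The size cannot be taken from the documents. The 5.5%-24% rejection range, the variance ratios and the 9-12 point gaps rest on assumed imbalances, correlations, skip rates and group split, and serve only as illustration. Adjustment reduces confounding by measured initial severity; other differences between early and late presenters remain. With at most about 63 treated confirmed cases and a late group likely to be small, the severity result is exploratory either way. This is a worthwhile, nearly free improvement to a secondary analysis and does not affect the primary outcome.

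**What to change.** 1. Make the ordinal regression the main severity analysis, with post-dose severity as outcome and Day 0 severity of the same symptom as a covariate. Keep the chi-square as descriptive. Confirm from the recorded ingestion time that each Day 0 rating precedes the dose.
2. Add time from onset to Day 0 as a second covariate, and show the model with and without it. This time is part of the interval that defines the groups, so it will overlap with the group term.
3. Reconcile the two Day 7 anchors in Protocol V. In Section XI, name the post-dose day or window and the per-person summary. Carry the analysis into the SAP.
4. Code 0 only where the symptom section was completed and the symptom was not endorsed. Treat skipped items and an unsubmitted Day 7 form as missing, and report their number by group.
5. Report both group sizes and label the result exploratory.

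The cost is protocol and SAP wording, plus a check that the form can tell a skipped item from an absent symptom. No extra visits or data sources are needed. The statistical price is one or two more model terms in a small sample.

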A list of serious adverse events will be presented by shelter and by treatment v. intervention period. As defined in the study protocol, serious adverse events include death, a life-threatening reaction to the study drug (or placebo) or other study procedure, hospitalization, or significant or persistent disability or impairment. The incidence of SAE's (events/person-days of follow-up) will be presented both (1) overall and (2) by case v. non-cases. We will test for a difference in SAE rate between the two study periods (intervention v. control) using an exact Poisson test in R.

Baloxavir-resistant influenza transmission

Evidence of a strong intervention effect causing incidence of baloxavir-resistant influenza strains will be evaluated using linear mixed effects logistic regression. The unit of analysis will be influenza-positive tests, and the outcome will be binary: baloxavir-resistant or not baloxavir-resistant.

B5. Power sample size

Table 1. Sample size calculations: Number of clusters needed per arm for two-group cluster-randomized trial - Household intervention study

Effect size (% reduction in flu incidence)			
Power	0.30	0.40	0.50
0.80	57	84	129
0.90	76	112	172

All calculations above assume an ICC of 0.29, anticipated average (or actual) cluster size of 4, and a 15% transmission rate for flu.

Based on these calculations, an arm size of 250 households should be sufficient to detect a 30% reduction in flu incidence at 90% power.

B6. Endpoint Analyses

Primary Analysis

[figure not shown]
Question: Does this home-based self-test diagnostic tool and rapid treatment intervention lead to a large percentage of influenza-positive individuals initiating antiviral therapy within 48 hours of symptom onset?

Endpoint: Cumulative incidence of influenza virus infection

Measure of Association:
Cumulative Incidence (Attack Rate, Incidence Proportion)

$$\text{Cumulative Incidence} = \frac{\text{Number of participants that successfully initiate antiviral therapy within 48 hours of symptom onset (among participants who have a cough and self-test positive for influenza) during the October 2019-May 2020 influenza season}}{\text{Number of influenza-free participants at risk at } t_0 \text{ (baseline)}}$$

Relevant DAG

Exposure:

Exposed (Treatment) = Participants who develop cough and self-test positive
Unexposed (No treatment) = Participants who develop cough but self-test negative

Outcome:

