Success = Participant initiated on antiviral therapy within 48 hours of symptom onset
Failure = Participant is not initiated on antiviral therapy (**more than 48 hours** after symptom onset *or* participant **never** initiates antiviral therapy)

Table 1. Estimated secondary attack rates for planned 2019-2020 study aim on household transmission dynamics.

The study is being conducted in the Seattle, WA area over one influenza season. The goal is to enroll at least 250 (up to 1,000) households. Of these, 25% are estimated to have an individual in the household diagnosed with influenza based on estimates from previous household studies.^{23, 28-29}

A table for influenza attack rates by household size is provided below.

Household attack rate	Total households enrolled	Primary cases	Secondary cases (mean household size 5)	Secondary cases (mean household size 4)	Secondary cases (mean household size 3)
25%	250	63	45-96	34-72	23-48

20%	250	50	36-76	27-57	18-38
10%	250	25	18-38	14-29	9-19
Mean household size includes case.					
Secondary attack rate 18-38%, secondary cases presented as a range based on these high and low bounds.³⁰⁻³²					

Incidence Density

Using time-specific variables such as date of enrollment, weekly symptom diaries and questionnaires, Incidence Density (ID) will be calculated, defined with the following formula:

Incidence Density =

Number of participants that successfully initiate antiviral therapy within 48 hours of symptom onset (among participants who have a cough and self-test positive for influenza)

Total person-days

Model

The proportion of individuals that 1) test positive and 2) receive and initiate treatment within 48 hours of symptom onset using home-based self-test and delivery methods will be analyzed with a binomial regression GLMM with a log link. The outcome follows a binomial distribution, with the number of successes in a series of n independent Bernoulli trials, where each trial has probability of success p . Successes here are defined as an individual successfully initiated on antiviral therapy within 48 hours of symptom onset using home-based self-test to diagnose influenza and home delivery of antivirals. The model is defined below:

Incidence proportions of influenza will be presented in tables.

A formal statistical comparisons between study periods (control vs. intervention) will be performed using a Wald test of the hypothesis

$H_0: RR=1$

$H_a: RR \neq 1$

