Question: Does influenza incidence change when we look at varying testing timepoints (e.g. testing within 24, 48, and 72 hours of symptom onset)?

Details:

A sensitivity analysis will be performed to assess the effect of delayed testing on the intervention effect. The model will be re-run with three subsets of the data: those that were treated within 24, 48, and 72 hours of symptom onset. This will then be further analyzed with a time*age interaction. For example, we might expect that a 13-year-old might have more detectable RNA virus than an older adult at the same time point.

Data cleaning and software

All analyses will be performed in R version 3.6.1 using packages `'lme4'` and `'swCRTdesign'`.

C. Interim Analysis Plan

Original Plan

The DSMB will meet every month to review study progress and other issues as outlined below. In the proposed 6 month study, it is expected that the DSMB will meet X times.

Study progress and validity

At each monthly visit the DSMB will review data on enrollment, adherence of both households and household members, and all protocol violations. The DSMB will also compare the (pooled) observed influenza incidence rate to the (pooled) expected influenza rate to determine if the influenza incidence rate among study participants is at least as great as the incidence rate assumed in the study design, since incidence varies by influenza season. The DSMB will recommend any changes to the study design they believe are needed to ensure study validity.

Expected event rate: 150/1000 pdy in the control period and 120/1000 pdy in the intervention period; 135/1000 pdy overall.

Efficacy monitoring

Baloxavir-resistant influenza strain transmission

Additional testing and sequencing of non-influenza respiratory pathogens will also occur. Baloxavir resistance will be analyzed via interim analyses and monitored for the duration of the study. In the unlikely event that the incidence of the transmission of baloxavir-resistant strains of flu exceeds 20% of study participants, the study will be halted.

Tables and Figures

Table 1a. Sociodemographic characteristics of individual participants, SFS Household Intervention Study, 2019-2020 influenza season

Variable	Full sample n=	Cases only n=
Sociodemographic variables		
Age - median (range)		
Sex		
Male		
Female		
Race		
American Indian or Alaska Native		
Native Hawaiian or other Pacific Islander		
Black or African American		
White		
Multiple Races		
Other		
Prefer not to say		

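### The SAP's 24/48/72 h sensitivity re-runs select on the model's own outcome; the Protocol's Cox contrast by treatment time also lacks a time origin and entry time

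*Protocol*

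**What the plan says.** **SAP B6.** The outcome is defined as "Success = Participant initiated on antiviral therapy within 48 hours of symptom onset". Its complement is "Failure = Participant is not initiated on antiviral therapy", spelled out as starting too late or never starting. Under Sensitivity analysis the SAP then states: "The model will be re-run with three subsets of the data: those that were treated within 24, 48, and 72 hours of symptom onset". A time-by-age interaction is to follow. The question that this is meant to answer is worded differently: "Does influenza incidence change when we look at varying testing timepoints". The first sentence of detail also concerns delayed testing, not treatment. Elsewhere B6 words the outcome in two other ways: "Endpoint: Cumulative incidence of influenza virus infection" in the primary analysis, and "The proportion of individuals that 1) test positive and 2) receive and initiate treatment within 48 hours of symptom onset" in the Model paragraph.

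**Protocol XI.** For baloxavir recipients, "a Cox proportional hazards model will be used to calculate the hazard ratio, 95% confidence interval, and p-value for symptom duration by group", the groups being treatment within and after 48 h of onset. Resolution is "defined as the time when the influenza-positive participant reports experiencing no respiratory or systemic symptoms". The text gives the end of the interval but not its start, nor when a recipient comes under observation. Duration of RNA detection has the same gap. The SAP gives no method for symptom duration. The same 48 h split also carries a chi-square test and ordinal regression of severity, and an incremental cost-effectiveness ratio.

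**Protocol V.** Self-testing requires symptoms that are present and have lasted under 48 h, and drug qualification carries the same time limit. Delivery is planned 2-6 h after diagnosis, the dose is to be taken on receipt, and the time of ingestion is recorded.

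**The concern.** Restricting a model to people treated by a given hour, when its outcome is treatment by 48 h, conditions on the result. The re-runs would give trivial or inflated success proportions that could be read as robustness of the timeliness finding.

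The Cox contrast has a different problem. Someone dosed after 48 h had to be ill long enough to be diagnosed late, whereas someone dosed early did not. If time runs from onset and groups are fixed from time zero, the late group carries guaranteed illness time. Early treatment then appears to shorten illness even if it does nothing. The analyst would have to settle an unstated choice that affects the hazard ratio.

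**Working it through.** **1. The re-runs.** Applying the B6 outcome line to each subset:

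| Subset | Who is in it | Outcome |
|---|---|---|
| Treated by 24 h | early starters only | all successes |
| Treated by 48 h | all who meet the success definition | all successes |
| Treated by 72 h | the above plus starters at 48-72 h | failures are only the 48-72 h starters; never-treated and later starters are gone |

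With no variation in the outcome, a risk ratio or interaction is not estimable in the first two subsets.

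Illustration (assumed counts): 63 self-test-positive people, of whom 45 are treated by 48 h, 5 at 48-72 h and 13 never.
- Full denominator: 45/63 = 71%.
- 48 h subset: 45/45 = 100%.
- 72 h subset: 45/50 = 90%.
- Moving the cut-off to 72 h in the full denominator instead: 50/63 = 79%, which is a meaningful quantity.

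If the subsets were meant to be by testing time, 24 h against 48 h could be compared. A 72 h window would add nobody if the under-48 h self-test criterion in Protocol V is followed.

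**2. The Cox contrast.** The plan's only sizing figure reproduces: 250 × 0.25 = 62.5, taken as 63, and 1.96 × 0.5/√63 = 0.1235, or 0.12 rounded. That figure concerns the primary proportion; nothing is stated for this contrast. Also, 63 is expected confirmed cases, not recipients. Recipients are clinically diagnosed (Protocol X) and limited to one per household (Protocol II), so they could be fewer, or at most 250.

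Null simulation, with timing and duration assumed because the documents give neither: 100,000 recipients per setting; lognormal illness, log-SD 0.5 or 0.7; diagnosis uniform on 0-48 h, uniform on 12-48 h, or concentrated late (48 × Beta(3,1)); delivery uniform on 2-6 h; still ill at diagnosis; censored 7 days after diagnosis. The hazard ratio is for resolution, early versus late, with truth equal to 1:

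| Median illness (days) | Onset clock, no delayed entry |
|---|---|
| 2 | 1.32-1.52 |
| 3 | 1.13-1.26 |
| 4 | 1.05-1.15 |
| 5 | 1.02-1.10 |
| 7 | 1.00-1.05 |

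Across these settings, the onset clock with entry at first dose gives 0.98-1.02, and a clock started at first dose gives 0.71-1.01.

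A separate Weibull check (medians 60-120 h, shape 1-2, 20% assigned late, late dosing up to 54 or 72 h, 8,000 simulated per setting) gave 1.08-1.58 without delayed entry and 0.96-1.08 with it. At its 120 h median the uncorrected range was 1.08-1.45. So the bias at 5 days is small only if few illnesses are very short and late doses fall soon after 48 h.

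With 63 recipients (lognormal, medians 2, 3 and 5 days), the uncorrected split rejects a true null in 2.3-9.6% of runs, and the split with delayed entry in 4.3-7.0%. If all 63 resolve, the standard error of the log hazard ratio is 1/√(63·q·(1−q)): 0.63 at a late share q of 4.2% and 0.27 at 33%. A hazard ratio of 1.10 (log 0.095) is then at most 0.095/0.27 = 0.35 standard errors.

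**3. Size of the late group.** With delivery taking D hours (2 to 6):
- Diagnosis uniform from hour L to 48: late share D/(48−L). For L = 0 this is 2/48 to 6/48; for L = 12, 2/36 to 6/36. Times 63: 2.6 to 10.5, about 3-11.
- Diagnosis concentrated late: 1−(1−D/48)³ = 12% to 33%. Times 63: 7.6 to 20.8, about 8-21.

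**The case against.** **On the re-runs.** A reader might infer that the analysis cannot answer its question under any reading of the outcome. The documents do not support that. Protocol X separates clinical diagnosis from PCR confirmation, so treated people can be PCR-negative, and infection among them is not fixed by definition. Under the Model paragraph, the first two subsets would estimate the self-test-positive share of treated people. Neither quantity is timeliness or cumulative incidence, but neither is degenerate. The question and first detail sentence also speak of testing, and a 24 h versus 48 h testing comparison would be estimable. What stands is the failure under the stated success/failure definition, together with the conflict between testing and treatment.

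**On the Cox contrast.** Symptom duration naturally suggests onset as the origin, so the first-dose clock is hypothetical. Requiring complete freedom from respiratory and systemic symptoms makes a 2-day median the least natural setting. A reader might infer a serious false-positive problem: with 250 recipients and a 2-day median, null rejection is 22-39%. That needs a treated case in every household, whereas the Protocol plans for 25%. The timing hypotheses in Protocol III concern severity and RNA duration, not symptom duration, and the bias for RNA duration was not computed. These points limit the size of the problem. They do not supply the missing entry rule, and onset is exactly the clock that needs one.

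**On the late group.** A reader might infer that it must be a handful and that its formal tests should go. The Protocol gives no timing distribution, treats the feasibility of 48 h treatment as unknown, and claims no power here. Whether to test formally is a judgement, not an error.

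**Conclusion.** The SAP sensitivity analysis is wrong as written. Under the outcome definition in B6, the 24 h and 48 h subsets contain only successes and the 72 h subset removes all never-treated failures. This follows from the text and needs no assumption.

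The Cox gap is real but secondary. On the onset clock without delayed entry, a null effect appears as a hazard ratio of about 1.3-1.5 at a 2-day median, 1.1-1.3 at 3 days, and close to 1 at 5-7 days in the main simulation. These sizes rest on assumed diagnosis times, delivery and illness distributions. With about 63 recipients the consequence is mostly a modest shift in an imprecise estimate.

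The small late group is only a caveat: about 3-11 or 8-21 of 63, depending on when people present, and more if delivery or ingestion is delayed. None of this touches the primary endpoint.

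**What to change.** **SAP B6, Sensitivity analysis.** Keep the full primary denominator, never-treated included, and vary the outcome: initiated within 24, 48 and 72 h. Name one outcome for the model. Reconcile *testing* with *treated*, and the 72 h testing window with the self-test criterion in Protocol V. Protocol III and SAP B6 word the denominator differently; this change applies to whichever is retained. The cost is wording only.

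**Protocol XI, Cox contrast.** Keep the 48 h split, state symptom onset as the origin, and use delayed entry at first dose. If resolution is known only to the day, enter at the end of the dosing day, among those still symptomatic. State origin and entry for RNA duration too. Ingestion time is already collected. The cost is that recipients who recover before entry drop out: with end-of-day entry, 23-34% at a 2-day median, 11-18% at 3 days, 2-8% at 5 and 1-3% at 7. Treatment delay is not randomised, so the estimate stays observational.

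**Optional supplement.** Continuous delay may be added, with the same entry rule, but need not replace the split. With 63 recipients and medians of 3 and 5 days, its power is 21-46% against 3-8% for the split if the resolution hazard is multiplied by 0.60 per 24 h of delay. It is 9-24% against 10-46% if the hazard halves at 48 h. Both effects are assumed.

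**Reporting.** Give the number treated after 48 h beside the severity and cost contrasts.
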